7.6.4 Other Analyses

Not applicable.

7.6.5 Interim Analyses

No formal interim analyses of unblinded data are planned.

8 Data Quality Assurance

The study will be conducted in accordance with the International Council for Harmonisation (ICH) GCP and the appropriate regulatory requirement(s). The investigator will receive training regarding the appropriate use of the investigational product as described in the protocol and the Investigator's Brochure.

The investigator is required to prepare and maintain adequate and accurate case histories designed to record all observations and other data pertinent to the study for each study patient. Study data will be entered on a electronic case report form (eCRF) by site personnel using a secure, validated, web-based electronic data capture (EDC) application. Ixcelsius and Ixcelsius-authorized representatives will have access to all data upon entry in the EDC application.

Study monitors will discuss instances of missing or uninterpretable data with the investigator so these can be resolved. Any changes to study data will be made to the eCRF and documented via an electronic audit trail associated with the affected eCRF.

8.1 Case Report Forms and Source Documents

The term CRF should be understood to refer to either a paper form or electronic data record or both, depending on the data collection method used in this study. This study is expected to use a web-based EDC application. Ixcelsius or designee will supply eCRFs for each patient screened. Historical information and study data, specified in the protocol, will be recorded on the eCRFs by the investigator or designee. All patient data from each study visit must be collected on source documents and must be promptly entered on the eCRFs in accordance with the specific instructions given. Case report form entries will be performed by an investigator or designee and the study coordinator, who are authorized to complete such documentation. It is the investigator's responsibility to ensure completion and to review and approve all eCRFs. Case report forms must be signed by the investigator or by an authorized staff member. These signatures serve to attest that the information contained on the CRFs is true. At all times, the investigator has final personal responsibility for the accuracy and authenticity of all clinical and laboratory data entered on the eCRFs.

Patient source documents are the physician's patient records maintained at the study site.

In some cases, the eCRF may also serve as the source document. In these cases, Ixcelsius (or designee) and the investigator must prospectively document which items will be recorded in the source documents and for which items the eCRF will stand as the source document.

If queries are generated by Ixcelsius or designee to the participating medical institutions for resolution, the eCRF data will be changed or a response will be recorded in accordance with the specific instructions given.

The investigator must maintain source documents, such as all original signed ICFs, laboratory reports, and complete medical history. All source documents should be accessible for verification by the site monitor, auditor, IRB, or for inspections by regulatory authorities. Direct access to these documents must be guaranteed by the investigator or designee. If electronic records are maintained at the medical institution, the method of verification must be specified in documents within that medical institution.

9 Ethics

9.1 Institutional Review Board

It is the responsibility of the investigator to have prospective approval of the study protocol, protocol amendments, informed consent, and other relevant documents, eg, recruitment advertisements, if applicable from the IRB. The study will commence only after the IRB has given full approval and the investigator has received the approval documents. All correspondence with the IRB should be retained in the investigator file. Copies of IRB approvals will be forwarded to Ixchelsis Ltd. Documentation of the IRB compliance with ICH GCP will be maintained by the site and will be available for review by Ixchelsis Ltd or its designee.

9.2 Ethical Conduct of the Study

The study will be conducted in accordance with all appropriate regulatory requirements, local laws, and under the IRB-approved protocol. The study will be conducted in accordance with current ICH GCP, all appropriate patient privacy requirements, and the ethical principles outlined in the Declaration of Helsinki.

9.3 Patient Information and Consent

A written informed consent in compliance with US Title 21 Code of Federal Regulations Part 50 shall be obtained from each patient before entering the study or performing any unusual or nonroutine procedure that involves risk to the patient. The investigator or subinvestigator (designated by the investigator) will fully explain the nature of the study to each patient using the IRB-approved informed consent document prior to each patient entering the study. The investigator or subinvestigator will explain the nature, purpose and methods, reasonably anticipated benefits, and potential hazards of the study to each patient in simple terms using the IRB-approved consent document. The investigator or subinvestigator will obtain written informed consent from each patient before any study specific activity is performed. The investigator will retain the original of each patient's signed consent form.

The ICF must be in compliance with ICH GCP, local regulatory requirements, and legal requirements.

The ICF and any changes made during the course of the study must be prospectively approved by both the IRB and Ixchelsis before use.

10 Investigator's Obligations

10.1 Confidentiality

To maintain patient privacy, all eCRFs, study drug accountability records, study reports, and communications will identify the patient by initials where permitted and/or by the assigned patient number. The patient's confidentiality will be maintained and will not be made publicly available to the extent permitted by the US Food and Drug Administration and applicable laws.

10.2 Study Conduct

The investigator will conduct the study in compliance with the protocol provided by Ixcelsius and given approval/favorable opinion by the IRB and the appropriate regulatory authority. Modifications to the protocol are not to be made without agreement of both the investigator and Ixcelsius. Changes to the protocol will require written IRB approval/favorable opinion before implementation, except when the modification is needed to eliminate an immediate hazard or hazards to patients. Ixcelsius or a designee will submit all protocol modifications to the appropriate regulatory authority(ies) in accordance with the governing regulations.

When immediate deviation from the protocol is required to eliminate an immediate hazard or hazards to patients, the investigator will contact Ixcelsius or a designee, if circumstances permit, to discuss the planned course of action. Any departures from the protocol must be documented.

10.3 Records Retention

To enable evaluations and/or audits from regulatory authorities or Ixcelsius, the investigator agrees to keep records, including the identity of all participating patients (sufficient information to link records, eg, CRFs, hospital records), all original signed ICFs, source documents, and detailed records of treatment disposition. The study documents should be retained until at least 2 years after the last approval of a marketing application in an ICH region and until there are no pending or contemplated marketing applications in an ICH region or at least 2 years have elapsed since the formal discontinuation of clinical development of the investigational product. These documents should be retained for a longer period, however, if required by the applicable regulatory requirements or by an agreement

with the sponsor. It is the responsibility of the sponsor to inform the investigator/institution as to when these documents no longer need to be retained. The investigator and institution should take measures to prevent accidental or premature destruction of these documents.

If the investigator relocates, retires, or for any reason withdraws from the study, Ixcelsius should be prospectively notified. The study documents must be transferred to an acceptable designee, such as another investigator, another institution, or to Ixcelsius. The investigator must obtain Ixcelsius's written permission before disposing of any records, even if the retention requirements have been met.

10.4 Publications

All information regarding IX-01 supplied by Ixcelsius to the Investigator is privileged and confidential information and Ixcelsius retains ownership of all data.

Following completion of the study, the data from the entire study may be considered for reporting at a scientific meeting or for publication in a scientific journal, in which case Ixcelsius will be responsible for these activities and will work with the Investigator to determine how the manuscript is written and edited, the number and order of authors, the publication to which it will be submitted, and other related issues. Authorship will be based on criteria stipulated by leading clinical journals (eg, contribution to 1 or more areas of study design, data analysis and interpretation, and manuscript preparation and review).

11 Study Management

11.1 Monitoring

Monitoring and auditing procedures will be followed to comply with ICH GCP guidelines. All information recorded on the eCRFs for this study must be consistent with the patient's source documentation. During the course of the study, the study monitor will make study site visits to review protocol compliance, verify eCRFs against source documentation, assess drug accountability, and ensure that the study is being conducted according to pertinent regulatory requirements. The review of medical records will be performed in a manner that ensures that patient confidentiality is maintained. The investigator and institution will allow Ixcelsius monitors or designee and appropriate regulatory authorities direct access to source documents to perform this verification.

It is important that the investigator(s) and relevant personnel are available during the monitoring visits and possible audits or inspections and that sufficient time is devoted to the process.

13.1 Appendix 1: Schedule of Events

Table 13-1 Schedule of Events

IX-0105 Study Schedule and Events							
	For Patients on Chronic SSRIs only Prescreening Visit ¹ (Week -8)	Visit 1 ¹ Screening (Week -4)	Visit 2 ² Baseline (Week 0)	Visit 3 ² (Week 2)	Visit 4 ² (Week 4)	Visit 5 or Early Termination ² (Week 8)	Visit 6 Follow Up (Week 10)
Days Post First Dose (Window)	-56	-28 (±3)	0 (±7)	14 (±3)	28 (±7)	56 (±7)	70 (±7)
Informed Consent	X	X ¹					
Medical History and Demography	X	X ¹					
Inclusion/Exclusion Criteria and Eligibility Review	X	X	X ³				
Physical Examination		X	X	X	X	X	X
Height		X					
Weight		X	X			X	X
Blood Pressure and Heart Rate		X	X		X	X	X
Oral Temperature			X				
12-lead ECG (single)		X	X			X	X
Safety Laboratory Tests (Clinical Chemistry, Hematology, and Coagulation ⁴)		X	X	X	X	X	X
Urinalysis		X	X		X	X	X
Serology (HBsAg, HCV Ab, HIV 1, HIV 2)		X					
Urine Drug Screen		X	X			X	
Randomization			X				
e-Diary Supply ⁵		X	X	X	X		
Diary Evaluation ⁵			X	X	X	X	
Study Drug Supply			X	X	X		
Study Drug Compliance				X	X	X	
IIEF ⁶			X		X	X	
PEP ⁶ (with additional question)			X		X	X	

IX-0105 Study Schedule and Events							
	For Patients on Chronic SSRIs only Prescreening Visit ¹ (Week -8)	Visit 1 ¹ Screening (Week -4)	Visit 2 ² Baseline (Week 0)	Visit 3 ² (Week 2)	Visit 4 ² (Week 4)	Visit 5 or Early Termination ² (Week 8)	Visit 6 Follow Up (Week 10)
Days Post First Dose (Window)	-56	-28 (±3)	0 (±7)	14 (±3)	28 (±7)	56 (±7)	70 (±7)
PGIS			X		X	X	
CGIC						X	
PHQ-9			X	X	X	X	
Columbia-Suicide Severity Rating Scale ⁷			X	(X)	(X)	(X)	(X)
Adverse Events			X	X	X	X	X
Concomitant Medications	X	X	X	X	X	X	X

Abbreviations: CGIC, Clinical Global Impression of Change; ECG, electrocardiogram; HBsAg, hepatitis B surface antigen; HCV Ab, hepatitis C virus antibody; HIV, human immunodeficiency virus; IELT, intravaginal ejaculatory latency time; IIEF, International Index of Erectile Function; PEP, Premature Ejaculation Profile; PHQ-9, Patient Health Questionnaire 9; SSRI, selective serotonin reuptake inhibitor.

1. Only patients taking chronic SSRIs will have an additional 4-week washout prior to the 4-week run-in period. They will attend a Prescreening Visit and will return to the site for a complete screening (Visit 1) once their washout period is complete. Informed consent and medical history will be obtained at the Prescreening Visit for patients who are receiving chronic SSRIs.
2. Refer to the Study Training Manual for instructions if a patient does not remember to return the LogPad.
3. The patient will return the LogPad to the investigator. The LogPad will provide a summary of the IELT data collected during the run-in period, and will indicate whether the patient is eligible to continue in the study based on the IELT criteria
4. Coagulation (prothrombin time and activated partial thromboplastin time) will be tested at baseline (Visit 2). Only prothrombin time will be taken at other time points if certain laboratory test criteria defined in Section 4.2 are fulfilled.
5. Medication use, IELT, ejaculation control, and ejaculation-related distress and alcohol intake are collected after each event via e-diary.
6. IIEF and PEP have 4-week recall periods, and so these questionnaires are completed by the patients at study visits as above.
7. Columbia-Suicide Severity Rating Scale is only mandatory at baseline but may be administered at other visits if clinically indicated.

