21. Mean systolic cuff blood pressure >140 mm Hg, as assessed by 3 measurements taken in sequence within 5 to 10 minutes of last measure.

22. Mean diastolic cuff blood pressure >90 mm Hg, as assessed by 3 measurements taken in sequence within 5 to 10 minutes of the last measure.
23. Significant psychiatric disease and/or risk of suicidal tendency as assessed by clinical evaluation and PHQ-9 and C-SSRS.
 - PHQ-9 total score >9 and/or score of >0 on Question 9 of PHQ-9 would be exclusion criterion.
24. Any other major medical or psychological or psychiatric condition that could cause the patient to be unsuitable for the study or could interfere with interpretation of the study results.
25. Clinically significant abnormal laboratory function test results (including liver enzymes $>2 \times$ the upper limit of normal [ULN] or bilirubin $>1.5 \times$ ULN).
26. Patients taking CYP3A4 inducers, or moderate and potent CYP3A4 inhibitors.
27. History of or other evidence of recent alcohol or drug abuse.

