5.6 Prior and Concomitant Therapy

Use of SSRIs must be stopped, and patients who were previously taking SSRIs regularly require an additional 4-week washout prior to the 4-week run-in period. Patients who require SSRI treatment for depression or other illnesses (not PE) should not be included in the study.

Concomitant treatment with PDE5 inhibitor (eg, sildenafil, tadalafil, vardenafil), topical anesthetics, and/or tramadol is prohibited. Additionally, any history (current or last 6 months) of use of Botox or similar product to treat PE is not allowed.

The following treatments are also prohibited during the study: monoamine oxidase inhibitors, alpha blockers, 5-alpha reductase inhibitors (including finasteride [Propecia] for hair loss). Herbal supplements are also prohibited.

Concomitant use of potent or moderate CYP3A4 inhibitors (eg, ketoconazole, itraconazole, ritonavir) and inducers (eg, bosentan, carbamazepine, phenytoin, phenobarbital, St John's Wort, and rifampicin) is not allowed from at least 4 weeks before the start of dosing until the end of the study.

6 Study Assessments and Procedures

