6.1 Study Visits

A complete listing of study measurements and evaluations may be found in the Schedule of Events (Table 13-1).

Screening Visit 1

Approximately 28 days (± 3 days) prior to the first dosing, patients will attend the center for assessment of eligibility for the study. Written informed consent must be obtained from each potentially eligible patient by study site personnel prior to the initiation of screening procedures as outlined in this protocol.

Note: Patients taking chronic SSRIs for the treatment of PE must have an additional 4-week washout prior to the 4-week run-in period.

After providing signed written informed consent, patients will complete screening assessments. Each patient who undergoes screening for study enrollment will be assigned an identification number, which will provide a means of identifying each patient. Information and data collected will include the following:

- Assessment of patient eligibility according to the entry criteria, including clinical interview by the Investigator or his/her qualified designee to indicate that the patient meets the ISSM definition of PE. In particular, the investigator should ask the patient about the duration of the symptoms of PE, since lifelong PE can only be diagnosed if ejaculation always or nearly always occurred prior to or within about 1 minute of vaginal penetration from the earliest sexual experience.
- Medical history and assessment of concomitant medication.
- Year and month of birth, gender at birth, and race (ethnicity).
- Height, weight and physical examination. A physical examination will be conducted by the Investigator or other licensed study site personnel to establish an overall profile of the

patient's health and to identify and document any abnormal physical findings prior to the patient's participation in the study.

- Recording of vital sign data (heart rate and blood pressure measurements).
- 12-lead ECG.
- Blood sampling for laboratory safety tests (including hematology and clinical chemistry analyses) and serology for HBsAg, HCV Ab, HIV 1, and HIV 2.
- Urinalysis.
- Urine drug screen.

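### For men on a chronic SSRI for PE, exclusion 23's PHQ-9 cut-offs are not scheduled to be applied until Visit 2, after the SSRI has been withdrawn for the trial

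*Combined protocol and SAP*

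**What the plan says.** **Washout.** Section 5.6 states: "Use of SSRIs must be stopped, and patients who were previously taking SSRIs regularly require an additional 4-week washout". It also bars men who need the drug for something else: "Patients who require SSRI treatment for depression or other illnesses (not PE) should not be included in the study". Footnote 1 to Table 13-1 (Section 13.1) places the washout between Prescreening and Visit 1: "They will attend a Prescreening Visit and will return to the site for a complete screening (Visit 1) once their washout period is complete". It adds: "Informed consent and medical history will be obtained at the Prescreening Visit for patients who are receiving chronic SSRIs". Besides consent and medical history, the Prescreening column is marked only for the eligibility review and concomitant medications. Section 6.1 has no Prescreening entry.

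**Instruments.** In Table 13-1 the PHQ-9 and C-SSRS rows are empty at Prescreening and Visit 1 and begin at Visit 2. Section 6.1 agrees: neither is listed for Screening Visit 1, and both are listed for Baseline Visit 2. Section 7.6.3 gives the PHQ-9 times as baseline and Weeks 2, 4 and 8.

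**Criteria.** Exclusion 23 (Section 4.1.2) reads: "Significant psychiatric disease and/or risk of suicidal tendency as assessed by clinical evaluation and PHQ-9 and C-SSRS". Its numeric part concerns the PHQ-9 alone: "PHQ-9 total score >9 and/or score of >0 on Question 9 of PHQ-9 would be exclusion criterion". The C-SSRS has no numeric cut-off. Exclusion 24 adds a general clinical ground: "Any other major medical or psychological or psychiatric condition that could cause the patient to be unsuitable for the study". Section 3.1 makes the C-SSRS mandatory at baseline and otherwise on a PHQ-9 trigger or at the investigator's discretion.

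**The concern.** Stopping the SSRI is something the trial requires, and for these men it comes before any scheduled use of the depression and suicidality instruments that the protocol relies on to exclude patients. A man who would score above the PHQ-9 cut-off at Week -8 could stop his SSRI, complete a four-week washout and a four-week run-in, and only then be found ineligible.

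The man at risk is one whose SSRI was prescribed for PE and whose depression or suicidality has not been recognised. Section 1.1 itself lists depression among the possible consequences of PE. What is at stake is his safety during withdrawal, not the trial's inference.

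**Working it through.** **Inputs.** Table 13-1: Prescreening Day -56 (no window printed), Visit 1 Day -28 (±3), Visit 2 Day 0 (±7). Sections 3.1 and 5.6: four-week washout, then four-week run-in. Section 13.2.4: the PHQ-9 asks about the last two weeks.

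1. **The plan's own figure.** Washout plus run-in = 28 + 28 = 56 days, which reproduces Day -56 for Prescreening.

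2. **Prescreening to first PHQ-9 and C-SSRS.** Nominal: 0 - (-56) = 56 days. With the Visit 2 window: -7 - (-56) = 49 and 7 - (-56) = 63. Neither end is a firm limit. Exclusion 2 allows screening to be extended, so the interval can be longer. At the lower end, a washout ending on Day -28 would leave a run-in of only -7 - (-28) = 21 days, short of four weeks.

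3. **When the SSRI stops.** No day is stated. For a man still taking it at Prescreening, with Visit 1 on Day -28 and a 28-day washout, the stop falls at -28 - 28 = Day -56, that is, at Prescreening. The conclusion does not depend on the exact day: footnote 1 has washout complete by Visit 1, and both instruments start at Visit 2. Scheduled PHQ-9 or C-SSRS assessments before withdrawal: 0.

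4. **What the Visit 2 PHQ-9 looks back on.** Nominally Day -14 to Day 0. With Visit 2 at its earliest, Day -7, recall reaches back to -7 - 14 = Day -21. Washout is over by Visit 1, at the latest -28 + 3 = Day -25. Recall therefore covers 0 of the 28 washout days.

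5. **Whether other text brings the screen forward.** Section 6.2 speaks of completing the PHQ-9 on the LogPad at each study visit. Section 6.1 first issues the LogPad at Visit 1, so that wording reaches at most a visit after washout. The interview specified for Visit 1 has another purpose: "clinical interview by the Investigator or his/her qualified designee to indicate that the patient meets the ISSM definition of PE". The mandatory C-SSRS trigger outside baseline is a PHQ-9 result, and none is scheduled before Visit 2 to set it off.

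6. **Gain from repeating the PHQ-9 at Visit 1.** Nominal: 0 - (-28) = 28 days sooner than Visit 2. If the SSRI stops no earlier than Day -56 and washout takes 28 days, Visit 1 cannot precede Day -28. Within the printed windows the gain is therefore at most 7 - (-28) = 35 days.

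**The case against.** The strongest reply is that men are not taken off an SSRI unassessed. History, medication review and eligibility review are all marked at Prescreening. Exclusion 23 has a clinical-evaluation limb, exclusion 24 covers other psychiatric conditions, and men who need an SSRI for another illness are barred. The C-SSRS may be given whenever the investigator sees cause. Section 6.3.1.1 has staff record changes in condition once consent is signed, and Visit 1 is in person. At Visit 2 the C-SSRS looks back over lifetime and past months.

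Most of this stands, and it rules out the stronger readings.

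- A reader might infer that there is no psychiatric safeguard before withdrawal. The documents do not support that. The safeguards exist; they are clinical or discretionary and have no scheduled instrument or score.
- A reader might infer that men could receive IX-01 unscreened. They could not under the schedule. Both instruments are completed at Visit 2 before dosing, which meets the purpose given in Section 1.5.
- A reader might infer that the results are compromised. Nothing here touches an endpoint, the sample size or the error rate.

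It can also be said that adding a questionnaire to a clinical evaluation is a matter of preference, and that a man still on his SSRI may score low. Both points limit the benefit. Neither removes the ordering problem: the plan makes a PHQ-9 score an exclusion, yet schedules the trial-driven withdrawal before that score is obtained.

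**Conclusion.** The point holds as a minor patient-safety improvement for one subgroup. For men still taking a chronic SSRI for PE at Prescreening, the PHQ-9 cut-offs are first scheduled to be applied nominally 56 days later, after withdrawal, and that PHQ-9 does not look back on the washout.

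This assumes that the SSRI is stopped at or after Prescreening, as footnote 1 implies, and that the washout lasts 28 days. The schedule reading is firm; the size of the benefit is not. The number of men affected is not given and may be small: Section 1.1 says patients are often reluctant to start off-label SSRIs, and the wording of Section 5.6 may include men who had already stopped. No detection yield is claimed. The 88% sensitivity and specificity quoted in Section 6.3 are not shown to apply to men taking an SSRI.

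**What to change.** In Table 13-1, and in a new Prescreening entry in Section 6.1, schedule the existing PHQ-9 at Prescreening before the SSRI is stopped. Use paper, because the LogPad is first issued at Visit 1, and say so, since Section 6.3 specifies completion on the LogPad. If the total is above 9 or Question 9 is above 0, do not start washout; administer the C-SSRS and carry out clinical review or referral at the same visit.

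Optionally, repeat the PHQ-9 at Visit 1 for these men as a post-washout safety check, with the C-SSRS trigger already in Section 3.1. This finds a problem sooner but cannot prevent the withdrawal. Leave the Visit 2 eligibility reading as it is.

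**Cost.** A nine-item form at one or two existing visits for this subgroup only, and an occasional face-to-face C-SSRS by trained staff. Some men would be excluded at Prescreening who might have scored 9 or less by Visit 2. Men whose scores are low while on the SSRI would still be missed at Prescreening.
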